#### **8.1.4 Interim Analysis**

No efficacy interim analyses are planned for Cohort B2 or Cohort D in this trial. However, an interim analysis for Cohort A, B or C may be performed if the rate of enrollment is much slower than anticipated during the course of the trial. An interim analysis for each cohort would only be performed in this study when  $\geq 10$  subjects in the respective cohort have had post-baseline scans through Week 16. Results will be reviewed by the study team. [Table 10](#) summarizes the strategy and timing of the potential interim analysis for each cohort.

For Cohort A, if an interim analysis is conducted and 2 or fewer subjects out of the first 10 subjects with post-baseline imaging scans (Week 16) have a confirmed or unconfirmed response, then enrollment may be paused until response data for the subsequent imaging scan (Week 24) are reviewed for subjects already enrolled in the trial. Enrollment may be resumed if the binomial probability of the observed response rate is  $\geq 80\%$  under the assumption of a  $\geq 20\%$  true response rate (e.g.,  $\geq 4/16$  confirmed or unconfirmed response).

For Cohorts B (HPV negative subjects only) and C, if an interim analysis is conducted and 1 or fewer subjects out of the first 10 subjects with post-baseline imaging scans (Week 16) have a confirmed or unconfirmed response, then enrollment may be paused until response data for the subsequent imaging scan (Week 24) are reviewed for subjects already enrolled in the trial. Enrollment may be resumed if the binomial probability of the observed response rate is  $\geq 80\%$  under the assumption of a  $\geq 10\%$  true response rate (e.g.,  $\geq 2/16$  confirmed or unconfirmed response). No interim analysis will be performed for the subjects with HPV positive head and neck cancer in Cohort B.

Although safety monitoring will occur continuously in the study, an assessment of Grade 4/5 drug-related immunologic AEs will be performed after 10 subjects have been enrolled within each cohort for 1 cycle of therapy. Enrollment will be paused if 4 or more subjects out of the first 10 subjects within a cohort experience a Grade 4/5 drug-related immunologic adverse event. Enrollment may be resumed within a cohort only after a full safety evaluation is performed in consultation between the study investigators and the Sponsor.

Table 10 Summary of Interim Analysis Strategy

Interim Analysis Number	Key Endpoints for Interim Analysis	Timing (Sample Size) for Analysis	Purpose of Analysis
Interim Analysis Cohort A	
 
• ORR
 
	
 
• <math>\geq 10</math> subjects with post-baseline scans (Week 16)
 
	
 
• Pause enrollment until further evidence of efficacy
 
• Pause enrollment for safety based on Grade 4+ drug-related immunologic AEs out of first 10 subjects
 

Interim Analysis Cohort B (HPV negative subjects only)	
 
• ORR
 
	
 
• <math>\geq 10</math> subjects with post-baseline scans (Week 16)
 
	
 
• Pause enrollment until further evidence of efficacy
 
• Pause enrollment for safety based on Grade 4+ drug-related immunologic AEs out of first 10 subjects
 

Interim Analysis Cohort C	
 
• ORR
 
	
 
• <math>\geq 10</math> subjects with post-baseline scans (Week 16)
 
	
 
• Pause enrollment until further evidence of efficacy
 
• Pause enrollment for safety based on Grade 4+ drug-related immunologic AEs out of first 10 subjects
 

## 8.2 Statistical Analysis Plan

### 8.2.1 Responsibility for Analyses/In-House Blinding

The statistical analysis of the data obtained from this study will be the responsibility of the Clinical Biostatistics department of the SPONSOR.

This trial is being conducted as an open-label study, i.e., subjects, investigators, and SPONSOR personnel will be aware of subject treatment assignments after each subject is enrolled and treatment is assigned. Access to the PD-L1 subject-level biomarker results for subjects in Cohort B2 for the purpose of summary reporting of PD-L1 level until the time that a clinical study report (CSR) is generated will be limited to an unblinded SPONSOR statistician and unblinded SPONSOR statistical programmer who will be responsible for data review to ensure validity of results and summary reporting of clinical response by biomarker status, but who will have no other responsibilities associated with the study.

The Clinical Biostatistics department will generate the allocation schedule(s) for study treatment assignment. Allocation will be implemented in an interactive voice response system (IVRS).

## **8.2.2 Hypotheses/Estimation**

Objectives and hypotheses of the study are stated in Section 3.0.

## **8.2.3 Analysis Endpoints**

Efficacy and safety endpoints that will be evaluated for within- and/or between-treatment differences are listed below, followed by the descriptions of the derivations of selected endpoints.

### **8.2.3.1 Efficacy/Immunogenicity/Pharmacokinetics Endpoints**

Efficacy and safety endpoints that will be evaluated for are listed below, followed by the descriptions of the derivations of selected endpoints.

The primary efficacy endpoint is response rate, defined as the proportion of subjects in the analysis population who have complete response (CR) or partial response (PR) using RECIST 1.1 criteria at any time during the study. Response for the primary analysis for cohorts A, B, C, D and B2 will be determined by a central independent radiology review. Secondary analyses will be based on the responses as assessed by the investigator.

Key secondary efficacy endpoints include:

- RECIST 1.1 response rate among HPV positive subjects.
- Response rate based on site assessments using RECIST 1.1.

Other secondary efficacy endpoints include: (1) duration of response, defined as time from first RECIST 1.1 response to disease progression in subjects who achieve a PR or better; (2) progression-free survival (PFS), defined as the time from allocation to the first documented disease progression according to RECIST 1.1 or death due to any cause, whichever occurs first; and (3) overall survival (OS).

### **8.2.3.2 Safety Endpoints**

A description of safety measures is provided in Section 4.2.3.2.

The primary safety endpoints are AEs graded using CTCAE (Version 4.0) criteria. Safety will be assessed by quantifying the toxicities and grades experienced by subjects who have received MK-3475, including serious adverse events (SAEs) and events of clinical interest (ECIs). Immune-related ECIs, as described in Section 7.2.3.2 will be collected. Other safety endpoints include laboratory safety assessments, ECOG performance status, vital signs and physical examinations.

## **8.2.4 Analysis Populations**

### **8.2.4.1 Efficacy Analysis Populations**

The Full Analysis Set (FAS) population will serve as the primary population for the analysis of efficacy data in this study. The FAS population consists of all randomized subjects in each Cohort who:

- Receive at least one dose of study treatment,
- Have a baseline scan with measurable disease per RECIST 1.1 by independent central radiology review, and
- Have a post baseline scan OR discontinue the trial due to progressive disease/drug related AE

For secondary by Investigator assessment, measurable disease for inclusion in the FAS population will be defined using Investigator assessment of the baseline scan.

A supportive analysis using the All Subjects as Treated (ASaT) population, defined as all randomized subjects, who received at least one dose of study treatment, will be performed for the primary efficacy endpoint(s).

Subjects will be included in the treatment group to which they are randomized for the analysis of efficacy data. Details on the approach to handling missing data are provided in Section 8.2.5 Statistical Methods.

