## **5.8 Subject Withdrawal/Discontinuation Criteria**

Subjects may withdraw consent at any time for any reason or be dropped from the trial at the discretion of the investigator should any untoward effect occur. In addition, a subject may be withdrawn by the investigator or the Sponsor if enrollment into the trial is inappropriate, the trial plan is violated, or for administrative and/or other safety reasons. Specific details regarding discontinuation or withdrawal procedures; including specific details regarding withdrawal from Future Biomedical Research, are provided in Section 7.1.4 – Other Procedures.

A subject must be discontinued from the trial for any of the following reasons:

- The subject or legal representative (such as a parent or legal guardian) withdraws consent.

A subject must be discontinued from treatment (but may continue to be monitored in the post-treatment follow-up portion of the trial) for any of the following reasons:

- The subject or legal representative (such as a parent or legal guardian) withdraws consent for treatment
- Confirmed radiographic disease progression

*Note:* For unconfirmed radiographic disease progression, please see Section 5.2.2.

*Note:* A subject may be granted an exception to continue on treatment with confirmed radiographic progression if clinically stable or clinically improved, please see Section 7.1.2.5.1.

- Unacceptable adverse experiences as described in Section 5.2.1.2
- Intercurrent illness that prevents further administration of treatment
- Investigator's decision to withdraw the subject
- The subject has a confirmed positive serum pregnancy test
- Noncompliance with trial treatment or procedure requirements
- The subject is lost to follow-up
- Completed 24 months of treatment with MK-3475

*Note:* 24 months of study medication is calculated from the date of first dose. Subjects who stop MK-3475 after 24 months may be eligible for up to one year of additional study treatment if they progress after stopping study treatment provided they meet the requirements detailed in Section 7.1.5.2.1.

- Administrative reasons

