The End of Treatment and Follow-up visit procedures are listed in Section 6 (Protocol Flow Chart) and Section 7.1.5 (Visit Requirements). After the end of treatment, each subject will be followed for 30 days for adverse event monitoring (serious adverse events will be collected for 90 days after the end of treatment or 30 days after the end of treatment if the subject initiates new anticancer therapy, whichever is earlier, as described in Section 7.2.3.1). Subjects who discontinue for reasons other than progressive disease will have post-treatment follow-up for disease status until disease progression, initiating a non-study cancer treatment, withdrawing consent or becoming lost to follow-up. After documented disease progression each subject will be followed by telephone for overall survival until death, withdrawal of consent, or the end of the study, whichever occurs first.

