### **5.9 Subject Replacement Strategy**

Additional subjects may be enrolled in a given cohort to ensure that the required number of evaluable subjects in each cohort is achieved. A subject that discontinues the trial for progressive disease or a drug-related AE will not be replaced and will be counted in the evaluable population of subjects for the respective cohort. Further details are provided in Section 8.1.3.

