#### **8.1.1 Efficacy Analyses**

The full analysis set (FAS) population (defined as all subjects with a baseline scan with measurable disease; by independent central radiology review for each cohort, and who either have a post baseline scan or discontinue the trial due to progressive disease or a drug-related AE) will serve as the primary population for the analyses of efficacy data in this trial. Supportive analyses of efficacy will be conducted in the all subjects as treated (ASaT) population and the FAS population by Investigator review. For each cohort, overall response rate will be used as the primary endpoint for efficacy assessment. A 95% confidence interval along with a one-sided p-value for testing the null hypothesis based on the binomial distribution will be provided for the response rate in each cohort. The respective cohort is considered to have reached the efficacy objective if the corresponding p-value for testing the respective null hypothesis is less than 2.5%. An outline of the efficacy analysis strategy is presented in [Table 9](#) below.

Table 9 Primary Analysis Strategy for Efficacy Endpoints

Endpoint/Variable‡ (Description, Time Point)	Statistical Method	Analysis Population	Missing Data Approach
Primary:			
Overall RECIST 1.1 response rate based on independent central radiology review (Cohort A, Cohort B HPV negative subjects, Cohort C, and Cohort D evaluated separately)	Exact test of binomial parameter	FAS	Subjects with missing data are considered non-responders
Overall RECIST 1.1 response rate based on independent central radiology review for subjects in Cohort B2	Exact test of binomial parameter	FAS	Subjects with missing data are considered non-responders
Secondary:			
Overall RECIST 1.1 response rate based on independent central radiology review, Cohort B HPV positive subjects,	Exact test of binomial parameter	FAS	Subjects with missing data are considered non-responders
Overall RECIST 1.1 response rate based on independent central radiology review, Cohort D AP subjects.	Exact test of binomial parameter	FAS	Subjects with missing data are considered non-responders
Overall RECIST 1.1 response rate based on based on independent central radiology review, for subjects previously treated with cetuximab and platinum in Cohorts B and B2	Exact test of binomial parameter	FAS	Subjects with missing data are considered non-responders

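### The FAS and the replacement rule turn on leaving the trial, but Section 5.8 makes progression and unacceptable AEs mainly reasons to stop treatment, so some early failures without a scan could fall out of the ORR denominator

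*Combined protocol and SAP*

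**What the plan says.** **FAS.** Section 8.2.4.1 requires at least one dose, centrally confirmed measurable disease at baseline, and that subjects "Have a post baseline scan OR discontinue the trial due to progressive disease/drug related AE". Section 8.1.1 has the same rule: subjects "who either have a post baseline scan or discontinue the trial due to progressive disease or a drug-related AE". The FAS is the primary efficacy population. Under 8.1.1 a cohort succeeds if its one-sided exact p-value is below 2.5%.

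**Replacement.** Section 5.9: "A subject that discontinues the trial for progressive disease or a drug-related AE will not be replaced and will be counted in the evaluable population".

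**Leaving the trial and leaving treatment.** Section 5.8 separates the two.
- Under "A subject must be discontinued from the trial for any of the following reasons" the only entry is withdrawal of consent.
- A second list opens with "A subject must be discontinued from treatment (but may continue to be monitored in the post-treatment follow-up portion of the trial" and contains "Confirmed radiographic disease progression" and unacceptable adverse experiences.
- The opening paragraph of 5.8 also lets a subject "be dropped from the trial at the discretion of the investigator should any untoward effect occur".
- On what follows progression, 5.8 says: "After documented disease progression each subject will be followed by telephone for overall survival until death, withdrawal of consent, or the end of the study".

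**Other relevant rules.** Imaging is every 8 weeks. The flow charts (6.1 footnote y, 6.2 footnote v) ask for a scan at treatment discontinuation when progression is not confirmed, but do not make it mandatory if a scan was done in the 4 weeks before. Section 8.2.5.1 counts missing response as non-response within the FAS. Section 8.2.4.1 adds a supportive ASaT analysis of the primary endpoint.

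**The concern.** The second limb of the FAS exists to keep early failures in the denominator when they never reached a scan. It is tied to an event, leaving the trial, that 5.8 does not normally produce for progression or a drug-related AE. Two examples show the gap:

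1. A subject deteriorates clinically at Week 4, stops drug, has no scan, and goes on to survival calls.
2. A subject has a drug-related Grade 4 event at Week 3, stops drug, and dies at Week 7 without a scan.

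Neither has left the trial because of progression or the AE in the sense of 5.8. A programmer who follows the text would leave both out of the FAS, and 5.9, worded the same way, would not bar replacing them. The missing-as-non-response rule cannot bring them back, because it applies only to subjects already in the FAS. If the investigator uses the discretionary removal in 5.8, the same history puts the subject in. Membership of the primary denominator would then depend on how an open-label site records disposition. Every subject lost this way is a non-responder, so the error can only raise the ORR.

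**Working it through.** **1. Reproduce the design.** Inputs are n, the success count k, the null rate p0 and the alternative p1 from Section 8.2.7. Formula: alpha = P(X ≥ k), X ~ Binomial(n, p0); power is the same tail at p1.

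| Cohort | k/n | p0 | p1 | Exact alpha | Exact power | Plan's power |
|---|---|---|---|---|---|---|
| A | 10/26 | 20% | 45% | 0.0232 | 0.806 | about 80% |
| B HPV negative, C | 6/22 | 10% | 35% | 0.0182 | 0.837 | about 80% |
| D | 10/32 | 15% | 40% | 0.0156 | 0.884 | about 90% |
| B2 | 11/100 | 5% | 20% | 0.0115 | 0.994 | >99% |

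The rules hold at 2.5%. Power for B HPV negative and C is somewhat above the stated figure, which does not matter here.

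**2. Who is affected.** A subject with any post-baseline scan enters by the first limb. That covers everyone with radiographic progression. What remains is a stop for clinical progression or a drug-related AE, with no post-baseline scan and no removal from the trial.

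**3. Type I error under the literal reading.** Let f be the share of otherwise eligible treated subjects in that group. The plan does not give f; 5%, 10% and 20% are assumptions. These subjects have no response, so if the ORR among all is p0, the ORR among those retained is p0/(1 − f).

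- *With replacement:* P(X ≥ k), X ~ Binomial(n, p0/(1 − f)). Cohort A at f = 10%: 0.20/0.90 = 0.2222, and P(X ≥ 10 of 26) = 4.6%.
- *Without replacement:* the retained number is Binomial(n, 1 − f), and the exact p < 0.025 rule is applied at each realised number.

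| Cohort | As designed | With replacement, f = 5 / 10 / 20% | Without replacement, f = 5 / 10 / 20% |
|---|---|---|---|
| A | 2.3% | 3.2 / 4.6 / 9.1% | 2.4 / 2.9 / 5.7% |
| B HPV negative, C | 1.8% | 2.3 / 2.9 / 4.8% | 1.8 / 2.0 / 3.2% |
| D | 1.6% | 2.2 / 3.1 / 6.3% | 2.0 / 2.9 / 5.0% |
| B2 | 1.15% | 1.6 / 2.3 / 4.8% | 2.7 / 2.9 / 5.7% |

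At 5%, only A with replacement and B2 without replacement exceed 2.5%. At 10%, B2 with replacement and B/C without replacement stay below it. At 20%, every entry exceeds it.

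**4. Cross-check with a fixed number dropped.** If one early failure in Cohort A is dropped and replaced, 27 subjects supply the 10 responses: P(X ≥ 10 of 27 at 20%) = 0.030. With three, P(X ≥ 10 of 29) = 0.049.

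**5. Results near the boundary.** In B2, 10/100 gives p = 0.0282 and fails; 10/99 gives 0.0265 and still fails; 10/98 gives 0.0249 and succeeds. In D, 9/32 gives 0.0413, 9/30 gives 0.0278, and 9/29 gives 0.0223. So two dropped subjects can change the outcome in B2 and three in D, but only at these counts. By contrast, 11 responses among all 110 planned B2 subjects still give p = 0.0221.

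**The case against.** The strongest reply is that this is loose terminology with a clear meaning. Section 5.9 says such subjects count as evaluable and are not replaced. Sections 1.0 and 5.8 also speak of subjects who discontinue and then enter post-treatment follow-up, where only treatment can be meant. That supports the intended reading, but 5.9 uses the same phrase as the FAS and so does not settle it in the text.

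A reader might infer that the second limb keeps nobody. The documents do not support that: the discretionary removal in 5.8 lets an untoward effect end trial participation, and such a subject would be kept.

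The group is also narrow. A scan is requested at discontinuation, and 8-weekly imaging should continue after a stop without documented progression. This stands, with limits. The request is not mandatory when a scan falls within the previous 4 weeks, which for a very early stop can be the baseline scan, and a subject who dies first has none.

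Finally, the ASaT analysis counts every dosed subject and would expose any difference. That is right and lowers the consequence, but success is judged on the FAS p-value.

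**Conclusion.** The mismatch is real and sits in the definition of the primary population. Followed literally, it drops some known early non-responders and allows their replacement, against the evident intent of 5.9. The direction is certain: ORR can only rise. The size is not known. It rests on an assumed share of 5% to 20%, on zero response in that share, and on the literal reading being the one applied. Across that range type I error runs from close to its design value to 9.1% (Cohort A, 20%, replaced).

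Two stronger conclusions are tempting and should not be drawn. The documents do not show a planned exclusion of early failures. Nor do they show that the 2.5% limit is breached in every cohort: at 5% most entries in the table stay within it. This is a wording defect that should be corrected before the FAS is programmed.

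**What to change.** In 8.1.1, 8.2.4.1 and 5.9, replace the reference to discontinuing the trial with: *discontinue(s) trial treatment due to progressive disease (radiographic or clinical) or a drug-related AE, whether or not they remain in follow-up*. These subjects then count as evaluable non-responders and are not replaced, and the success counts in 8.2.7 need no change.

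The cost is a wording change in three sections. The reported ORR may be slightly lower than under the literal rule.

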### **8.2.4.2 Safety Analysis Populations**

The All Subjects as Treated (ASaT) population will be used for the analysis of safety data in this study. The ASaT population consists of all allocated subjects who received at least one dose of study treatment.

At least one laboratory or vital sign measurement obtained subsequent to at least one dose of study treatment is required for inclusion in the analysis of each specific parameter. To assess change from baseline, a baseline measurement is also required.

Details on the approach to handling missing data for safety analyses are provided in Section 8.2.5 Statistical Methods.

## **8.2.5 Statistical Methods**

Statistical testing and inference for safety analyses are described in 8.2.5.2. Efficacy results that will be considered to be statistically significant after consideration of the strategy for controlling the Type I error are described in Section 8.2.6, Multiplicity. Nominal p-values may be computed for other efficacy analyses as a measure of strength of association between the endpoint and the treatment effect rather than formal tests of hypotheses. Unless otherwise stated, all statistical tests will be conducted at the  $\alpha=0.05$  (2-sided) level.

### 8.2.5.1 Statistical Methods for Efficacy Analyses

Efficacy will be evaluated separately in each cohort. For the primary efficacy endpoint independent centrally reviewed RECIST 1.1 response rate, the point estimate, exact 95% Clopper-Pearson confidence interval, and p-value for testing the RECIST 1.1 response rate is greater than the historical control for each cohort will be provided using exact binomial distribution. Subjects in the primary analysis population (FAS) without response data will be counted as non-responder.

Secondary efficacy evaluations of RECIST 1.1 response based on Investigator assessment will also be conducted using the same methodology as for the primary efficacy analysis. Efficacy for the secondary analysis of RECIST 1.1 response by independent central radiology review among subjects with HPV positive head and neck cancer will be evaluated in the same manner as in the primary analysis.

For PFS endpoint, Kaplan-Meier (KM) curves and median estimates from the KM curves will be provided as appropriate. Subjects without efficacy evaluation data or without survival data will be censored at Day 1. [Table 11](#) summarizes the key efficacy analyses.

Table 11 Analysis Strategy for Key Efficacy Variables

Endpoint/Variable ‡ (Description, Time Point)	Statistical Method	Analysis Population	Missing Data Approach
Overall RECIST 1.1 response rate based on independent central radiology review (Cohort A, Cohort B HPV negative subjects, Cohort C, and Cohort D evaluated separately)	Exact test of binomial parameter	FAS (Primary) ASaT (Supportive)	Subjects with missing data are considered non-responders
Overall RECIST 1.1 response rate based on independent central radiology review for subjects in Cohort B2	Exact test of binomial parameter	FAS (Primary) ASaT (Supportive)	Subjects with missing data are considered non-responders
Overall RECIST1.1 response rate based on independent central radiology review, Cohort B HPV positive subjects,	Exact test of binomial parameter	FAS (Primary) ASaT (Supportive)	Subjects with missing data are considered non-responders
Overall RECIST 1.1 response rate based on independent central radiology review, Cohort D AP subjects.	Exact test of binomial parameter	FAS (Primary) ASaT (Supportive)	Subjects with missing data are considered non-responders
Overall RECIST 1.1 response rate based on based on independent central radiology review, for subjects previously treated with cetuximab and platinum in Cohorts B and B2	Exact test of binomial parameter	FAS (Primary) ASaT (Supportive)	Subjects with missing data are considered non-responders
Overall RECIST 1.1 response rate based on investigator assessment for cohorts A,B, C and D	Exact methods for binomial parameter	FAS (Primary) ASaT (Supportive)	Subjects with missing data are considered non-responders
Overall RECIST 1.1 response rate based on investigator assessment for Cohort B2	Exact methods for binomial parameter	FAS (Primary) ASaT (Supportive)	Subjects with missing data are considered non-responders

Endpoint/Variable‡ (Description, Time Point)	Statistical Method	Analysis Population	Missing Data Approach
Progression-free survival	Summary statistics using Kaplan-Meier method	FAS(Primary) ASaT (Supportive)	Censored at last assessment
Overall survival	Summary statistics using Kaplan-Meier method	FAS(Primary) ASaT (Supportive)	Censored at last assessment
Response duration	Summary statistics using Kaplan-Meier method	All responders	Non-responders are excluded in analysis

The strategy to address multiplicity issues with regard to multiple efficacy endpoints is described in Section 8.2.6, Multiplicity and Section 8.2.9, Interim Analyses.

